11 STATISTICAL CONSIDERATIONS

11.1 DETERMINATION OF SAMPLE SIZE

Taking into consideration the current number of patients enrolled in the four parent studies, it is estimated that up to approximately 1,200 patients could be enrolled.

11.2 DISPOSITION OF PATIENTS

Screened patients are defined as any patient who originally met the inclusion criteria and signed the informed consent form.

Enrolled patients consist of all screened patients, with a treatment kit number allocated and recorded in the IVRS/IWRS database, regardless of whether treatment kit was used or not.

11.3 ANALYSIS POPULATIONS

11.3.1 Safety population

The Safety population considered for safety analyses will be the population who did actually receive at least one dose or partial dose of IMP in the current study.

11.3.2 Efficacy population

11.3.2.1 Modified Intent-to-treat population

The efficacy population considered for efficacy analyses will be the population of patients who received at least one dose or partial dose of IMP in the current study, with a baseline (from parent study) LDL-C available and with at least one LDL-C value available in the period from first IMP injection in the current study to last IMP injection + 21 days.

11.3.3 Other analysis population

The anti-alirocumab antibody analysis will be performed on all treated patients (safety population) with a blood sample on Week 0 (baseline from parent study) and at least one evaluable blood sample for antibodies post IMP injection in the current study.

11.4 STATISTICAL METHODS

11.4.1 Extent of alirocumab exposure and compliance

The alirocumab extent exposure and compliance will be assessed and summarized within the safety population.

In order to ensure the continuity of the investigational treatment for the patients without interruption (only in the event the manufacturer faces any performance or supply issues of the auto-injector), back-up plans may be implemented as described in Section 8.1. In that case, exposure to initial device and back-up device will be summarized and impact on study results will be assessed. More details will be provided in the SAP, if applicable.

11.4.1.1 Extent of investigational medicinal product exposure

The total exposure will be assessed by:

- Duration of alirocumab exposure in weeks defined as: (last alirocumab injection date + 14 -first alirocumab injection date) / 7, regardless of unplanned intermittent discontinuations.
- The total number of injections by patient.

11.4.1.2 Compliance

Compliance will be assessed using the following parameters:

• The mean injection frequency will be defined for each patient as the average number of days between 2 consecutive injections, that is: (last dose date – first dose date)/(number of injections -1).

This parameter will be summarized descriptively (N, Mean, SD, Median, Min and Max).

- The overall compliance will be defined for each patient as: 100 (% days with underplanned dosing + % days with above-planned dosing). Under-planned and above-planned dosing will be defined as follows, considering that injections should be performed every 2 weeks (+ 3 days):
 - The %days with under-planned dosing will be defined for each patient as the number of days with no injection administered within the previous 17 days divided by the duration of IMP injection exposure in days. For example, if a patient takes a dose 18 days after his/her previous injection, then 1 day is counted as a day under-planned dosing.
 - The %days with above-planned dosing will be defined for each patient as the number of days with more than one injection administered within the 11 days before divided by the duration of IMP injection exposure in days. For example, if a patient takes a dose 9 days after his/her previous injection, then 2 days are counted as a days above-planned dosing.

10-Jul-2015 Version number: 1

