8.1.2 Timing of administration

On Day 1, visit 1, patients from the ODYSSEY Long Term study will have the possibility to perform a placebo, self-injection training using an auto-injector, before the first alirocumab injection.

On the same day, the first alirocumab injection will be done at the site by the patient or another designated person (such as spouse, relative, etc) under direct site staff supervision. Patients will be monitored at the investigational site for at least 30 minutes after this first injection in this study.

Alirocumab subcutaneous injections will then be performed outside of the clinic, every two weeks up to the last injection planned in the protocol. If the injection is scheduled to take place on the same date as the site visit, then the IMP should be administered after the blood sampling has been completed.

Alirocumab should ideally be administered subcutaneously every two weeks at approximately the same time of the day. The time of the day is based upon patient's preference; however it is acceptable to have a window period of \pm 3 days.

If by mistake or due to other circumstances an injection is delayed:

- by more than 7 days or completely missed, then the patient should return to the original schedule of study treatment administration without administering delayed injections.
- by less than or equal to 7 days from the missed date, then the patient should administer the delayed injection and then resume the original schedule of study treatment administration.

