10.3.1 Temporary treatment discontinuation with investigational medicinal product(s)

Temporary treatment discontinuation (also referred to as treatment interruption) may be considered by the Investigator because of suspected AEs. Reinitiating of treatment with the IMP will be done under close and appropriate clinical and/or laboratory monitoring once the Investigator will have considered according to his/her best medical judgment that the responsibility of the IMP in the occurrence of the concerned event was unlikely and if the selection criteria for the study are still met (refer to Section 7.1 and Section 7.2).

All treatment interruption duration should be recorded by the Investigator in the appropriate e-CRF screens when considered as confirmed.

Treatment interruption is defined as one or more scheduled injections that are not administered to the patient as decided by the Investigator.

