#### 2.4.3.2 Compliance

Compliance will be assessed using the following parameters:

- The mean injection frequency of OLE IMP will be defined for each patient as the average number of days between 2 consecutive injections, that is: (last injection date first injection date)/(number of injections -1) for patients receiving at least 2 injections.
- The overall compliance for injections will be defined for each patient as: 100-(%days with under-planned dosing + %days with above-planned dosing). Under-planned and above-planned dosing will be defined as follows, considering that injections should be performed every 2 weeks (±3 days as per protocol):
  - the %days with under-planned dosing will be defined for each patient as the number of days with no injection administered within the previous 17 days divided by the duration of IMP injection exposure in days. For example if a patient takes a dose 18

25-Jan-2016 Version number: 1

days after his/her previous injection, then 1 day is counted as a day under-planned dosing.

- the %days with above-planned dosing will be defined for each patient as the number of days with more than one injection administered within the 11 days before divided by the duration of IMP injection exposure in days. For example if a patient takes a dose 9 days after his/her previous injection, then 2 days are counted as days above-planned dosing.

These parameters will be summarized descriptively (N, Mean, SD, Median, Minimum and Maximum).

The percentage of patients whose overall compliance for injections is <80% will be also summarized as well as numbers and percentages of patients with 0%, >0% and  $\leq$ 5%, >5% and  $\leq$ 10%, >10% and  $\leq$ 20%, and >20% days with above-planned dosing and numbers and percentages of patients with 0%, >0% and  $\leq$ 5%, >5% and  $\leq$ 10%, >10% and  $\leq$ 20%, and >20% days with underplanned dosing.

The overall compliance (quantitatively and by category (<80% vs  $\ge80\%$ )) will be also summarized by the following time periods:  $\ge0$  and  $<26, \ge26$  and  $<52, \ge52$  and  $<78, \ge78$  and  $<104, \ge104$  and  $<130, \ge130$  and <156, and  $\ge156$  weeks.

According to protocol, cases of overdose are reported in the AE e-CRF pages and will be described in the AE analysis (see Section 2.4.5.1 and Section 2.1.4.1).

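### Compliance is scored from gaps between injections rather than against the dosing schedule, so following the late-dose rule counts as above-planned dosing and the <80% flag is lenient for isolated missed doses near the cut-off

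*Protocol*

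**What the plan says.** **Dosing rule (protocol 8.1.2).** Injections are every two weeks, and "it is acceptable to have a window period of" ±3 days. If an injection is late by 7 days or less, "then the patient should administer the delayed injection and then resume the original schedule of study treatment administration". If it is later than that or missed, "then the patient should return to the original schedule of study treatment administration without administering delayed injections". Both branches bring the patient back to fixed dates.

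**Scoring rule (protocol 11.4.1.2, repeated in SAP 2.4.3.2).** Overall compliance is 100 minus the percentages of under-planned and above-planned days. Under-planned days are the "number of days with no injection administered within the previous 17 days"; above-planned days are "the number of days with more than one injection administered within the 11 days before". Both are divided by exposure in days. The SAP presents the tolerance as "3 days as per protocol", but applies it to the interval since the last injection and not to the schedule dates.

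**Use.** SAP 2.4.3.2 states: "The percentage of patients whose overall compliance for injections is <80% will be also summarized". It also plans five categories each of under- and above-planned days, and overall compliance by time period (26-week blocks, then 156 weeks onwards).

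**Interruptions (protocol 10.3.1).** "Treatment interruption is defined as one or more scheduled injections that are not administered to the patient as decided by the Investigator". Their duration is recorded in the e-CRF. The compliance sections make no separate provision for them.

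**The concern.** A table headed compliance will be read as adherence to the protocol's schedule. Under a gap rule, a patient who does what 8.1.2 says after a late dose collects both under-planned and above-planned days, and the above-planned label suggests more drug than intended when none was taken. In the other direction, the 3-day timing tolerance is also deducted from doses that were never taken, so missed doses are discounted. Interruptions ordered by the investigator are mixed with patient omissions.

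The primary objective is long-term safety, and exposure duration (protocol 11.4.1.1) disregards intermittent discontinuations. The compliance table is therefore one of the places a reader would look to see how much of the planned drug lies behind the safety results.

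**Working it through.** **Inputs.** Long-gap limit 17 days, short-gap limit 11 days (protocol 11.4.1.2). Exposure = last injection − first injection + 14 days (protocol 11.4.1.1). Late-dose rule of 7 days and ±3-day window (protocol 8.1.2). Cut-off 80% (SAP 2.4.3.2). Full-length treatment of 168 weeks (protocol 6.1) = 84 planned injections.

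**Formula.** Compliance = 100 − 100 × [Σ max(0, gap − 17) + Σ max(0, 11 − gap)] / exposure.

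**The plan's own examples.** An 18-day gap gives 18 − 17 = 1 under-planned day; a 9-day gap gives 11 − 9 = 2 above-planned days. Both are reproduced.

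**1. Patients who follow the dosing rules**
- One dose 7 days late, the next on schedule: gaps of 21 and 7 days, so 21 − 17 = 4 under-planned and 11 − 7 = 4 above-planned days. Over 84 doses compliance is 100 − 100 × 8/1176 = 99.3%.
- Every dose at a random whole day within ±3 days of its schedule date (assumption: uniform): overall compliance averages about 97% (range about 94% to 99%). Every simulated patient has some above-planned days, averaging 1.4% and about 3% at most. All fall in the category above 0% and up to 5%; the 0% category would be nearly empty.
- Strict alternation between 3 days early and 3 days late: gaps of 20 and 8 days cost 3 + 3 = 6 of every 28 days, a long-run score of 78.6%. Over 84 doses it is 78.7% to 79.1%, depending on the starting sign and whether Day 1 is fixed.
- A 7-day delay at every second dose: 71.9%.

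**2. Patients who miss doses**
- One isolated miss: gap of 28 days, cost 28 − 17 = 11 of the 14 days lost. With isolated misses only, compliance = 100 − (11/14) × % missed, so <80% requires more than 20 × 14/11 = 25.5% missed.
- Runs of misses are counted more fully: two in a row cost 25/28 = 89% of their days, three 39/42 = 93%, six 81/84 = 96%.
- Every fourth dose missed, exact-day dosing: 100 − 100 × 220/1162 = 81.1% if the 4th dose is the first missed; 100 − 100 × 231/1176 = 80.4% if it is the 2nd or 3rd. Injections taken: 63/84 = 75.0% (63/83 = 75.9% if counting stops at the last injection in the first case).
- The same pattern can fall below 80%. With ±3-day random timing and the 4th dose first missed, the mean is 79.6% and about 38% of simulated patients reach 80%. With exposure of 98 days and the 2nd dose first missed, it is 100 − 100 × 22/98 = 77.6%. A 26-week block containing four misses gives 100 − 100 × 44/182 = 75.8%.
- Doses missed independently at random over 84 planned (assumption), share of patients at or above 80%:

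| Missed | Gap rule, exact-day | Doses taken / planned |
|---|---|---|
| 5% | 100% | 100% |
| 10% | 100% | 99.7% |
| 20% | 85% | 50% |
| 22% | 72% | 33% |
| 35% | 2% | 0% |

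At 22% missed, adding ±3-day random timing lowers the gap-rule share from about 72% to about 55%. Simulated shares vary by a point or so between runs.

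**The case against.** **Gap scoring is a legitimate choice.** It describes dosing spacing, protocol and SAP agree on it, and both give worked examples. The protocol uses intervals elsewhere: a minimum of 11 days before OLE entry (10.1.1.1), and an overdose definition based on injections less than 7 days apart (10.4.4.1). This stands, and is why the gap measure should be kept. A pure schedule measure would treat a dose 7 days late followed by one 3 days early, a 4-day gap, as fully compliant.

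**Missed drug is already partly visible.** Total injections, mean injection frequency and the under-planned categories are planned. The every-fourth patient shows a mean interval of about 18.5 to 18.7 days and, over 168 weeks with exact-day dosing, falls in the category above 10% and up to 20%. This also stands and limits the harm. It does not correct the <80% flag or the above-planned label.

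**The window may not be centred on schedule dates.** Section 8.1.2 implies this but does not state it. The random-timing and alternation results depend on that reading; the late-dose result does not.

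**A reader might infer that the table ranks patients the wrong way round**, with adherent patients below 80% and those missing every fourth dose above it. The documents do not support that as a general statement. Falling below 80% without a miss needs near-extreme alternation or repeated long delays, and the every-fourth patient stays above 80% only in some circumstances.

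**Conclusion.** The mismatch is real and lies in the text: 8.1.2 works from a schedule, while the compliance rule works from the previous injection. Its firm consequences are that rule-following after a late dose is labelled above-planned, and that an isolated missed dose is counted at 11/14 = 79% of its length. The flag is therefore lenient near the cut-off: at 22% missed at random, about 72% (exact-day) or 55% (with timing variation) of patients pass, against about 33% on doses taken. At miss rates of 5% to 10% or 35% the two measures classify patients almost alike.

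These shares rest on independent random misses, full 168-week exposure and, for the second figure, uniform timing within ±3 days of schedule dates. The documents give no expected miss rate.

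A reader might also infer that the safety or efficacy conclusions are at risk. They are not on this ground: compliance is descriptive, defines no analysis population and enters no endpoint or test. This is a cheap improvement to a summary table.

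**What to change.** In SAP 2.4.3.2:

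- Add, for each patient and by time period, 100 × injections taken / injections planned on the 14-day schedule from first to last injection, stating how the last injection is matched to a schedule date. Apply the <80% cut to this figure.
- Show investigator-ordered interruptions, as recorded under protocol 10.3.1, on a separate line so that they can be told apart from other missed doses.
- Keep the 11/17-day measure as a spacing measure, relabelled as days with short interval and days with long interval. This keeps short gaps visible, including cases where an extra injection offsets a missed one in the count.

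Record the change in SAP 1.6 as a departure from protocol 11.4.1.2. The cost is wording and a little programming; injection dates and interruption durations are already in the e-CRF. The reported compliance figure will be slightly lower for patients who miss isolated doses.

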11.4.2 Analyses of safety endpoints

All safety analyses will be performed on the Safety population using the following common rule:

The baseline value is defined generally as the last available value before first injection. For analyses of changes from baseline for laboratory and vital signs parameters, baseline of the parent study or of the current study (ie value at visit 1 before the first injection) may be considered.

The safety analysis will focus on the Treatment Emergent Adverse Events (TEAE) period defined as the time from the first dose of the current study to the last dose of IMP + 70 days (10 weeks).

The following definitions will be applied to laboratory parameters and vital signs.

The potentially clinically significant abnormality (PCSA) values are defined as abnormal values considered medically important by the Sponsor according to predefined criteria/thresholds based on literature review and defined by the Sponsor for clinical laboratory tests and vital signs.

PCSA criteria will determine which patients had at least 1 PCSA during the TEAE period, taking into account all evaluations performed during the TEAE period, including unscheduled or repeated evaluations. The number of all such patients will be the numerator for the PCSA percentage.

Treatment period: the treatment period used for quantitative analysis is defined as the time from first dose of IMP injection to the last dose of IMP injection + 21 days.

AE definition:

- Pre-treatment AEs are AEs that developed or worsened or became serious during the PRE-TREATMENT period;
- Treatment-emergent AEs (TEAEs) are AEs that developed or worsened or became serious during the TEAE period;
- Post-treatment AEs are AEs that developed or worsened or became serious during the POST-TREATMENT period.

Drug-induced liver injury:

Liver function tests, namely ALT, AST, alkaline phosphatase and total bilirubin, are used to assess possible drug-induced liver toxicity. The proportion of patients with PCSA values at any post-baseline visit by baseline status will be displayed by treatment group for each parameter. A graph of distribution of peak values of ALT versus peak values of total bilirubin will also be presented. Note that the ALT and total bilirubin values are presented on a logarithmic scale. The graph will be divided into 4 quadrants with a vertical line corresponding to 3 x ULN for ALT and a horizontal line corresponding to 2 x ULN for total bilirubin.

The incidence of liver-related AEs will be summarized by treatment group. The selection of preferred terms will be based on standardized MedDRA query (SMQ) Hepatic disorder. Time to liver-related treatment discontinuation and time to liver death may also be provided based on hepatic disorder SMQ.

11.4.2.1 Adverse events

Adverse event incidence tables will present by system organ class (SOC) (sorted by internationally agreed order), high-level group term (HLGT), high level term (HLT) and preferred term (PT) sorted in alphabetical order, the number (n) and percentage (%) of patients experiencing an AE. Multiple occurrences of the same event in the same patient will be counted only once in the tables within a treatment phase. The denominator for computation of percentages is the safety population.

Adverse event incidence table will be provided for all types of TEAEs: all TEAEs, all treatment emergent AESI, all treatment emergent SAEs and all TEAEs leading to permanent treatment discontinuation.

If any clinically significant signal is detected and need further characterization or for adverse event of clinical interest, exploration of time to onset could be performed for these selected TEAEs as described below to account for the differential exposure time in all patients. Selected TEAEs will be also analyzed using time-to-event approach (Kaplan-Meier methodology). Time from the first dose of IMP injection to the first occurrence of the event will be calculated (only the first event will be counted). Patients without any event will be censored at the end of the TEAE period. Incidence rates at different time points of exposure will be presented and Kaplan-Meier curves will be provided.

Death:

The following deaths summaries will be generated:

- Number (%) of patients who died by study period (TEAE, on-study, post-study) summarized on the safety population
- TEAE leading to death (death as an outcome on the AE CRF page as reported by the Investigator) by primary SOC, HLGT, HLT and PT showing number (%) of patients sorted by internationally agreed order of SOC and alphabetic order of HLGT, HLT, and PT.

11.4.2.2 Laboratory data and vital signs

The summary statistics (including mean, median, Q1, Q3, standard error, minimum and maximum) of all laboratory variables, all vital signs parameters (raw data and changes from baseline) will be calculated for each visit, last and worst value assessed during the treatment period. For selected parameters, mean changes from baseline with the corresponding standard error will be plotted over time (at same time points).

The incidence of PCSAs at any time during the TEAE period (on-treatment PCSAs) will be summarized whatever the baseline level and/or according to the following baseline categories:

- Normal/missing
- Abnormal according to PCSA criterion or criteria

For laboratory parameters for which PCSA criterion is not defined, similar table(s) using the normal range could be provided.

11.4.3 Analyses of efficacy data

Efficacy variables will be explored through descriptive statistics at each scheduled visit of the current study.

Percent changes from baseline of the parent study and success rate to reach targets from week 8 time point will be analyzed all groups combined as influence of treatment received during the parent study should be offset by the treatment received during the current study after 8 weeks of treatment.

Percent changes, and when appropriate absolute change, from baseline of the parent study in calculated LDL-C, total-C, HDL-C, TG, and non-HDL-C will be summarized at each time point in the efficacy population using number of available data, mean, SD, median, minimum, and maximum. For percent change, 95% confidence intervals of the mean will also be provided. All measurements, scheduled or unscheduled, collected from week 8 up to 21days after the last IMP injection, will be assigned to analysis windows defined in the SAP in order to provide an assessment for these time points. Laboratory assessments other than the ones provided by the central laboratory will be excluded. For TG, measurements on not fasting patients will be excluded.

Same kind of tables (with either percent change from baseline or absolute change from baseline) will be provided for other efficacy parameters: Apo B, Apo A-1, ratio Apo B/Apo A-1, Lp(a).

For TG and Lp(a), summary statistics will include Q1 and Q3.

Success rate to reach the different targets defined for LDL-C in Section 9.2.1 will be provided with corresponding 95% confidence intervals.

